The Center of Disease Control and Prevention considers Antimicrobial Resistance as a global threat with millions affected worldwide. This occurs when microorganisms develop the ability to evade antimicrobials and can affect individuals at any stage of life. Antimicrobial-resistant infections requiring second-and third-line treatment alternatives can cause serious side effects such as organ failure, prolonged care and recovery, and even no treatment options for some cases. Surgical antibiotic prophylaxis is a high volume of antimicrobial use worldwide, and is a common area of antibiotic misuse9. Therefore, to reduce further emergence of antimicrobial resistance, and to preserve antimicrobial effectiveness in the future, surgical prophylaxis is an aspect of patient care in which antibiotic use should be optimized9. Guidelines recommend that Fluoroguinolones are the first line agent used as prophylaxis for transrectal biopsies, however. there has been an increased resistance of normal gut flora to Fluoroquinolones which may be the reason for increased incidence of post transrectal biopsy related infections despite antimicrobial prophylaxis⁸. Local resistance patterns in our institution shows an increasing resistance pattern to Cephalosphorins, which is the standard prophylactic regimen for transperineal prostate biopsies done at our hospital. Our Antimicrobial Stewardshop Program recommends Cefoxitin as the antibiotic of choice for prophylaxis for transrectal prostate biopsies. No recommendations has been set for transperineal prostate biopsies. For urologists, guidelines set by the Americal Urological Association on pre procedural antibiotics for transrectal prostate biopsies, which recommend a fluoroquinolone, or a 3rd generation Cephalosphorin is being followed. This is due to lack of standardized guidelines for transperineal prostate biopsies. Currently, all urologists give antibiotic prophylaxis in the form of a 2nd generation Cephalosphorin. No post procedural antibiotics are being given. The fear of sepsis previously experienced in transrectal biopsies still haunts urologists. Approximately 300 transperineal prostate biopsies are performed at our institution yearly, therefore, if the results of this study is positive, that would greatly reduce number of patients exposed to antibiotics. The effectiveness of Cephalosphorins are also decreasing, based on the hospital's antibiogram with increased emergence of esbl+ E. Coli strains obtained from genitourinary specimen cultures. Urologists deal with diseases of the urinary tract, and at times, these diseases are complicated by infections. Diseases such as in urolithiasis, Benign Prostatic Hyperplasia, Neurogenic bladders, and Catheter Associated Urinary Tract Infections all require the use of antimicrobials, and if the effectiveness of our current antibiotics are decreased due to resistant strains, then it becomes a health care burden for all. Results of this study can be useful in clinical practice, not only in Urology, but in other subspecialties as well. Given the limited health resources available in our country, actions of medical professionals should always be supported with high level evidence, such as this study. Addressing these knowledge gaps is crucial for improving antibiotic prophylaxis guidelines, enhancing patient outcomes, and reducing antibiotic resistance. This study would also promote judicious use of antibiotics, which may lessen

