Chronic Bacterial Prostatitis is a bacterial infection of the prostate lasting more than 3 months. Urine cultures are persistently positive for the same organism. E. coli is still the most common organism isolated. Patients present with recurrent or relapsing urinary tract infections, urethritis, or epididymitis with the same bacterial strain. Diagnosis is made through history or physical examination, Voiding test such as pre and post prostatic massage and a positive urine culture²⁸.

Asymptomatic prostatitis is diagnosed when inflammatory cells are identified incidentally on prostate biopsy on an asymptomatic patient. Treatment is catered based on the primary reason for urologic consultation. Further urologic evaluation is indicated if the reason for consult is an increased PSA²⁸.

Preoperative antibiotic prophylaxis is the administration of antibiotics before surgery to reduce the risk of post operative infection. Although the timing of antibiotic administration varies, the goal of preoperative systemic antibiotic prophylaxis is to maintain the highest tissue concentrations at baseline and during surgery. The literature recommends at least 30 minutes and no more than 60 minutes before skin incision to achieve the optimal time for preoperative administration of the most commonly used antibiotics²⁹.

Post biopsy infection is the Occurrence of Lower Urinary tract Infection symptoms such as frequency, dysuria, and urgency, or Severe Urinary Tract Infection such as loin pain, rigour and fever³. Microbiologic tests include a positive urinalysis, and urine culture. Occurrence of urosepsis, meeting a SOFA score of > 2 in the presence of a urinary tract pathogen, all of which occurring within 2 weeks post biopsy.

Objectives

General Objective

To compare incidence infectious complications in patients given antibiotic prophylaxis versus no prophylaxis among patients at St. Luke's Medical Center Global City and Quezon City from March 2024- January 2024

Specific Objective

- 1. To compare the incidence of urinary tract infection and sepsis between patients without and with antibiotic prophylaxis undergoing prostate biopsy.
- 2. To compare Hospital admissions, Emergency room visits, and non-infectious complications between the no prophylaxis versus prophylaxis groups.

Methods

Study design and setting

This will be a randomized controlled trial to be conducted at St. Luke's Medical Center Global City and Quezon City from June 2024 to June 2025.

Study population

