Method of subject assignment to study groups

The primary investigator will be the one to approach the potential participants for their informed consent. Among those who consented, They will be screened for eligibility, then randomized using a pre generated sequential list using an online application https://www.random.org/ either to group A (no antibiotic prophylaxis) and to group B (with antibiotic prophylaxis using 1g IV Cefoxitin).

Description of procedure/s for all study groups

Group A – Experimental Group

In the experimental group, patients will be given normal saline solution in a syringe, which is identical to syringes used to give antibiotics 1 hour prior to the procedure. Both solutions will be clear, which means neither patient or doctor will be aware of what was given as to avoid bias. Only the staff of the stone center will be aware of this. They will be instructed by the researcher or the consultant or research assistant to perform this one hour prior to the procedure just like giving prophylactic antibiotics.

Group B With Antibiotic Prophylaxis using Cefoxitin 2g IV

Patients will be given 2g IV of Cefoxitin 1 hour prior to the procedure.

After being given NSS or Cefoxitin, both groups will undergo transperineal prostate biopsy. Standard skin preparation will be done for both groups. Excessive hair is shaved off the perineum. The perineum is prepared using Betadine (10% povidone-iodine). The perineum is then prepped with betadine solution starting from the center of the perineum with 1 passage from inside to outside for 5 times Biopsy will then be performed. Biopsy procedure to be done is the standardized technique recommended by the American urologic Association, which involves a targeted (lesion centered) biopsy, followed by a systematic biopsy to get a representation of all parts of the prostate gland. After the procedure, the post biopsy site will be cleaned thoroughly using cutasept solution. The patient will then be awaken once the procedure is done, and will be sent to the recovery room for observation. Patients should void prior being discharged home. A temporary urinary catheter is placed if patients develop acute urinary retention. Patients will then be taught on the symptoms of UTI or sepsis and advised to seek medical attention if these occur.

Randomization and Blinding procedures

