Once the patient has given his signed consent, and patient is eligible to join the study, he will then be randomized into the experimental or control group using the online app https://www.random.org. The app generates a sequential list which prevents the investigator from learning allocation before a patient is registered into the study and from altering allocation afterwards, thus full concealment. Randomization will be performed by a research assistant not involved in the administration of treatments or data collection. The sequential list will be saved in a password protected file only accessible to the research assistant.. After a patient has been allocated, the group assignment will be permanent and unmodifiable. The randomization codes will be kept by the research assistant as well. Antibiotic or placebo will be administered by the stone center staff before the patient is put to sleep. The primary investigator will not be part of the biopsy procedure for blinding purposes.

Risks

One of the common side effects of prostate biopsy is infection. According to studies, 2% patients may experience mild disease not requiring hospitalization, and 1% may experience severe infections requiring hospitalization despite antibiotics. Based on literature, there will be no added risk of infection whether a patient is given antibiotics or not.

The most common side effect of antibiotic administration (Cefoxitin) is Diarrhea. Other rare side effects seen in less than 1% of patients given this drug includes Anemia, or decrease in hemoglobin, Increase in eosinophils in the blood, elevated liver enzymes, Decrease in platelets, and decrease in white blood cells. Patients who have allergies to antibiotics may also experience hypersensitivity reactions to this drug. There is also risk of alteration of the normal bacterial flora, which promotes antimicrobial resistance. This will decrease susceptibility of bacteria to antimicrobials making infections harder to treat.

Benefits

You will not receive direct benefits by participating in this study, however you may be spared from potential side effects of antibiotics. Furthermore, future prostate biopsy patients will benefit from enhanced guidelines on the need for prophylactic antibiotics to balance the risk of infection versus occurrence for antibiotic resistance.

Criteria for withdrawing subjects from the study and stopping the study as a whole

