Patients experiencing an adverse event such as symptoms of urinary tract infection like hematuria, dysuria, frequency, and urgency and systemic symptoms such as fever, generalized weakness, malaise will be evaluated right away initially with a complete blood count, urinalysis, and urine culture. Patients who will satisfy the criteria of Urinary Tract Infection, will be considered as having post biopsy infectious complications, and will be evaluated for possible sepsis. According to literature, 2% of patients undergoing prostate biopsy may experience mild post biopsy infection. 1% of patients may develop severe infections or urosepsis requiring hospitalization²². Computed sample size for the study is a total of 120 patients, with 60 patients in each arm. Hence, if more than 2 patients develop mild biopsy infection, and more than 1 patient develop severe infections from the experimental group, the study will be terminated and conclusion will be recommendation of administration of antibiotic prophylaxis. Patients who were not able to complete the procedure due to any circumstance, those who cannot tolerate anesthesia, those with adverse effects from anesthesia or antibiotics, and patients not compliant to follow up tests will be withdrawn from the study.

Data to be gathered

Patients who will pass the inclusion criteria will have their demographic data recorded such as age, sex, Height, Weight, BMI, Charlson Scores, Prostate volume, PSA, and History of Previous Biopsies. Post operatively, UTI will be assessed using a symptom checklist, which includes dysuria, urgency, frequency, or hematuria, fever, flank pain, nausea/vomiting. Signs of Systemic Inflammatory Response Syndrome (SIRS) will be gathered in patients who develop signs of urinary tract infection, namely, Temperature, Heart Rate, Respiratory Rate, White Blood Cell Count, and Blood Pressure. Incidence of sepsis and UTI In both groups will be recorded. Patients with Fever, or 2 or more signs of SIRS will be advised admission immediately. Histopathology results, 30 day readmissions, 30 day emergency room visit, and non infectious complications based on the Clavien Dindo classification will also be gathered.

Laboratory/assessment procedures to be performed

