A minimum sample of 60 patients per group is needed for a non-inferiority study with binary outcomes. Basourakos, et al reported that rates of post-biopsy genitourinary infections were 1.35% in the AP group and 1.22% in the NAP group²⁴. The target set was at least 80% power and 90% confidence interval. This was computed using Sealed Envelope Ltd. 2012. Power calculator for binary outcome non-inferiority trial. There are paucity of data regarding post prostate biopsy infections in patients without antibiotic prophylaxis. Similarly, data on post biopsy infections in Filipinos are lacking. A study reported by Yaddao, et al., published in the Philippine Journal of Urology, reported an infection rate of 5% occurring after biopsy, hence, we chose 5% as our non-inferiority limit.

Data Analysis

To assess the primary and secondary outcomes, we analyzed the 90% confidence interval (CI) of the difference in proportions, following Altman's recommendation. Non-inferiority was established if the upper bound of the 90% CI was less than 5%. Descriptive statistics, including median, percentages, 90% CI, or interquartile range (IQR), were reported as appropriate. For comparisons between groups, an independent t-test was used for continuous variables, while the chi-square or Fisher's exact test was applied for categorical variables. All statistical calculations were performed using MedCalc Statistical Software version 23.2.6

Ethical Considerations

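### The control-arm cefoxitin dose is 1 g in one section of the protocol and 2 g in the next, so the non-inferiority comparator is not fixed

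*Protocol*

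**What the plan says.** Three statements in the protocol give a dose for group B, the antibiotic arm:

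- *Method of subject assignment to study groups*: group B is "with antibiotic prophylaxis using 1g IV Cefoxitin".
- *Description of procedure/s for all study groups*, group B heading: "Group B With Antibiotic Prophylaxis using Cefoxitin 2g IV".
- The same section, group B text: "Patients will be given 2g IV of Cefoxitin 1 hour prior to the procedure".

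Two other sections name the drug without a dose. The rationale says that the hospital's stewardship programme "recommends Cefoxitin as the antibiotic of choice for prophylaxis for transrectal prostate biopsies", which concerns a different biopsy route. The *Risks* section lists the drug's side effects.

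The trial is a "randomized controlled trial to be conducted at St. Luke's Medical Center Global City and Quezon City". On administration, *Randomization and Blinding procedures* says: "Antibiotic or placebo will be administered by the stone center staff before the patient is put to sleep". The procedures section adds that these staff take their instruction from the researcher, the consultant or the research assistant.

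**The concern.** Cefoxitin is the only active treatment in the trial and the reference against which omission is judged, with a margin of 5 percentage points. In a non-inferiority trial the comparator gives the conclusion its meaning. If the protocol does not say which regimen the control arm receives, a reader cannot say what the no-prophylaxis arm was shown to be non-inferior to. The protocol hopes to inform international guidelines, where that question would be asked at once.

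There is also a practical risk. Two hospitals take part, and the instruction to give the drug may come from any of three roles. With two doses in the text and no rule to choose between them, nothing in the protocol prevents the dose from differing between patients or sites. This is a possibility and not something the protocol describes. Conflicting doses of an intravenous drug are a medication-safety discrepancy in any case.

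**Working it through.** **Step 1. Compare every mention of cefoxitin.**

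| Section | Dose for group B |
|---|---|
| Significance of the Project and Rationale | none given (refers to transrectal biopsy) |
| Method of subject assignment to study groups | 1 g IV |
| Description of procedures, group B heading | 2 g IV |
| Description of procedures, group B text | 2 g IV, 1 hour before the procedure |
| Risks | none given |

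The ratio is 2 g / 1 g = 2. All three dose statements describe the same arm and belong to the current text, not to a log of changes. No sentence ranks one above another, and none allows the dose to vary by patient or site. That 2 g appears twice and 1 g once does not settle the matter, because a count of mentions is not a rule of precedence.

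**Step 2. How many patients the instruction covers.** The section on withdrawal and stopping says: "Computed sample size for the study is a total of 120 patients, with 60 patients in each arm". The ambiguous instruction therefore applies to 60 planned control patients.

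**Step 3. Does the dose affect any stated statistical figure?** The sample size section says: "A minimum sample of 60 patients per group is needed for a non-inferiority study with binary outcomes". Its inputs are infection rates of 1.35% with prophylaxis (p_C) and 1.22% without (p_T), a margin d of 5 points, 80% power, and a 90% confidence interval, taken here as a one-sided alpha of 0.05. With unpooled variance:

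n per arm = [p_C(1 − p_C) + p_T(1 − p_T)] × (z₀.₉₅ + z₀.₈₀)² / [d − (p_T − p_C)]²

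- Variance term: 0.0135 × 0.9865 + 0.0122 × 0.9878 = 0.01332 + 0.01205 = 0.02537
- (1.645 + 0.842)² ≈ 6.18
- Denominator: (0.05 + 0.0013)² = 0.0513² = 0.002632
- n = 0.02537 × 6.18 / 0.002632 ≈ 59.6, rounded up to 60

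The plan's figure is reproduced. Dose is not an input, so reconciling it changes no sample size, power or alpha figure.

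**Step 4. Would the planned data reveal a difference in dose?** The items under *Data to be gathered* do not include the dose given. A standard data collection form is mentioned but not shown, so it may record the dose. The protocol text does not require it.

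**Step 5. Could patients already have been treated?** The version is dated 1/07/2025, the methods section plans a start in June 2024, and the data analysis section is written in the past tense. Treatment before this version is therefore plausible, and correcting the text alone would not show what was given.

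**The case against.** The best defence is that this is a slip in one parenthesis. The 1 g figure stands in a section about assignment, while the section that describes administration agrees with itself in heading and text. Staff are instructed by members of the study team and may never take a dose from the protocol. No patient is shown to have received an inconsistent dose, no statistical figure changes, and variation between patients or sites is inference.

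Much of this is fair. Dose variation is only a possibility, and the 60 patients measure the reach of the ambiguous instruction, not of any misdosing. It would also be wrong to argue from the protocol that the blind is weakened: it calls the saline and antibiotic syringes identical and both solutions clear, and it gives no volume for either dose.

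The contradiction itself remains. Those who instruct the staff need a dose, and the protocol gives them two. The agreement within the administration section does not show which dose was approved. A statistical analysis plan, if one exists, would not normally set a treatment dose, so the matter belongs in the protocol.

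**Conclusion.** The concern holds. The protocol is wrong as written: it gives two doses, differing two-fold, for the only active arm and non-inferiority comparator, and nothing resolves them. The instruction covers all 60 planned control patients.

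This conclusion rests only on the three dose statements, together with the absence of any sentence that decides between them. It does not assume that doses in fact varied. The effect on infection rates cannot be derived from the documents, and the sample size of 60 per arm is untouched. The point must be fixed because the control regimen cannot be identified from the text and because of the medication-safety discrepancy.

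**What to change.** 1. Reconcile the assignment section and the group B procedure section so that both state the single dose that was approved and is in use. The investigators must establish which that is from the approved documents.
2. If any patients have been treated, check the administration records at both hospitals for the dose actually given, and report any variation with the results.
3. Add the dose given to the listed data items and to the data collection form, if it is not already there.

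The cost is a one-line correction to the text, one data field and a check of administration records. No sample size or analysis figure needs to change.

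### The stopping rule fixes a recommendation for prophylaxis from Group A counts alone, separately from the trial's comparative criterion, and does not settle which counts trigger it

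*Protocol*

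**What the plan says.** In the Protocol, the section on criteria for withdrawing subjects and stopping the study quotes two background rates: "2% of patients undergoing prostate biopsy may experience mild post biopsy infection" and "1% of patients may develop severe infections or urosepsis requiring hospitalization". It then gives the size of the trial: "Computed sample size for the study is a total of 120 patients, with 60 patients in each arm". From these it derives a rule that applies "if more than 2 patients develop mild biopsy infection, and more than 1 patient develop severe infections from the experimental group". The consequence it attaches to that event is that "the study will be terminated and conclusion will be recommendation of administration of antibiotic prophylaxis".

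The Risks section gives the same two rates as rates seen under prophylaxis: "2% patients may experience mild disease not requiring hospitalization, and 1% may experience severe infections requiring hospitalization despite antibiotics". It adds that "there will be no added risk of infection whether a patient is given antibiotics or not".

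The Sample Size section plans a non-inferiority comparison with a 5-point margin, 80% power and a 90% interval, from a meta-analysis in which "rates of post-biopsy genitourinary infections were 1.35% in the AP group and 1.22% in the NAP group". The Data Analysis section declares non-inferiority when the upper 90% confidence limit for the difference in proportions is below 5%.

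**The concern.** The trial has two routes to a conclusion. One compares the arms. The other looks at Group A only and has its answer written in advance. By the protocol's own account infections also occur with antibiotics, at the same 2% and 1%, so a count in Group A cannot show that prophylaxis would have prevented those infections. At stake is a practice recommendation with no randomised comparison behind it. A statistical analysis plan could not repair this, because the protocol states the conclusion outright.

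The trigger itself is a second problem. The sentence joins its two limits with *and*, and it does not say whether a severe infection also counts towards the first limit. A rule meant to protect Group A may therefore respond poorly to severe infections. On another reading it may stop many trials in which nothing exceeds the quoted rates.

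**Working it through.** **Inputs.** Background rates of 2% mild and 1% severe, and limits of more than 2 (at least 3) mild and more than 1 (at least 2) severe, are from the stopping section. The 60 per arm is from the stopping and Sample Size sections. The margin of 5 points and the 90% interval are from the Sample Size and Data Analysis sections.

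**1. The plan's own figure.** With 1.35% and 1.22%, one-sided 5% and 80% power:

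n = (1.645 + 0.842)² × [0.0135×0.9865 + 0.0122×0.9878] / (0.05 + 0.0013)² = 59.6, so 60 per arm.

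The stated size is reproduced, and it is the size for the comparative criterion. The stopping rule has no stated operating figure to reproduce.

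**2. Where the limits could come from.** In 120 patients the expected counts are 0.02×120 = 2.4 and 0.01×120 = 1.2, which round down to 2 and 1. In 60 patients they are 1.2 and 0.6, which round up to 2 and 1. Both denominators give the printed limits.

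**3. Stopping section against Data Analysis section.** With separate counts, the smallest Group A result that triggers the rule is 3 mild + 2 severe = 5/60 = 8.33%. The protocol prints no interval formula, so I use Newcombe's, with Wald as a check:

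U = d + √[(uA − pA)² + (pB − lB)²], where l and u are 90% Wilson limits. For 5/60 these are 4.12% and 16.15%; for 8/60 they are 7.68% and 22.15%.

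- 5/60 in each arm: d = 0 and U = √(7.81² + 4.22²) = 8.9 points. By symmetry the interval is -8.9 to +8.9 (Wald -8.3 to +8.3). This is inconclusive.
- 5/60 in A, 8/60 in B: d = -5.0 and U = -5.0 + √(7.81² + 5.65²) = 4.6 points (Wald 4.3). Non-inferiority is met.
- 5/60 in A, 7/60 in B: U = 6.1 points (Wald 5.7). Non-inferiority is not met.

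The stopping section recommends prophylaxis in all three cases.

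**4. How often the rule fires.** Let M and S be the mild and severe counts in 60 patients, trinomial with rates pM and pS:

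P(M=m, S=s) = 60! / [m! s! (60−m−s)!] × pM^m × pS^s × (1−pM−pS)^(60−m−s)

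This is summed over the trigger region. Counts only rise, so the chance of ever firing equals the chance that the final counts exceed the limits.

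| Mild / severe rate | *and*, separate (M≥3 and S≥2) | *or* (M≥3 or S≥2) | *and*, severe also in first limit (M+S≥3 and S≥2) |
|---|---|---|---|
| 2% / 1% | 1.4% | 22.6% | 9.1% |
| 4% / 2% | 14.2% | 62.9% | 31.9% |
| 6% / 3% | 37.6% | 87.1% | 53.4% |
| 8% / 4% | 60.2% | 96.4% | 69.6% |
| 2% / 5% | 9.4% | 83.3% | 74.3% |
| 2% / 10% | 11.7% | 98.8% | 97.6% |

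Check on the first row: P(M≥3) = 11.9% and P(S≥2) = 12.1%, and 11.9 + 12.1 − 1.4 = 22.6%. In the last two rows the separate-count column cannot exceed P(M≥3) = 11.9%, however common severe infections become.

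**The case against.** **The two sections will seldom reach opposite answers.** This largely stands for the *and* rule. After 5 infections in Group A, non-inferiority is met only with at least 8 of 60 in Group B. The chance of that is about 0.04% at a true rate of 3% and about 0.00015% at the planned 1.35%. In nearly every realistic case where the rule fires, non-inferiority would fail anyway. But failing to show non-inferiority is not evidence that prophylaxis works, and the equal-arms case needs no excess in Group B. On the *or* reading, conflict also needs less: two severe cases suffice, and 2/60 against 4/60 gives an upper limit of 3.9 points (Newcombe).

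**The rule's apparent blindness to severe infections depends on how they are counted.** This stands. The stopping section first counts patients who meet the infection criteria and then evaluates those same patients for sepsis, so severe cases may belong in the first limit. On that reading the rule fires in 74.3% rather than 9.4% of trials at 2% mild and 5% severe. The text does not say which reading applies.

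**Stronger readings that the protocol does not support.**
- A reader might infer that the limits were computed for 120 patients and wrongly applied to 60. The section names both numbers and does not say which it used, and rounding gives 2 and 1 from either.
- A reader might infer that the rule almost never fires. That is true only at the background rates, where a stopping rule should seldom fire. At doubled to fourfold rates it fires in 14% to 60% of trials even with separate counts.
- A reader might infer that applying the rule must unblind the investigator. The Randomization and Blinding section gives the codes to the research assistant, and the Ethical Considerations section gives the Ethics Review Board access to all data. Group A counts can be had without the investigator. Who applies the rule, and its printed trigger probabilities, are details that another document may hold.

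**Conclusion.** The stopping sentence is wrong as written. It commits the trial to recommending prophylaxis from one arm, while the trial's declared criterion is a difference between arms. With 5/60 in each arm the data would support neither non-inferiority nor that recommendation. This part needs no assumption about how infections are classified; the worked intervals assume all 60 patients per arm are observed. An earlier stop would leave fewer patients in each arm and less information still.

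The trigger is also not fixed well enough to act on. At the quoted 2% and 1% its chance of firing is 1.4%, 9.1% or 22.6%, depending on the reading. These figures assume independent patients, full follow-up of Group A and both counts taken in Group A. The low sensitivity to severe infections holds only if mild and severe are separate counts, which the wording suggests but does not state. The denominator behind the limits is unstated, which is a gap in the text and not a demonstrated arithmetic error.

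**What to change.** Delete the predetermined conclusion. State that, if the trial stops, both arms and the 90% confidence interval for the difference will be reported, and that the conclusion will be only what this interval supports under the Data Analysis section.

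Reconcile the stopping sentence with its own 2% and 1% figures and with the 60 patients to whom it is applied. It should say:
- whether both limits or either one must be exceeded;
- whether severe cases also count towards the first limit;
- which denominator the limits were derived from.

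No particular threshold is proposed here. That choice belongs to the investigators and the ethics committee, and the table above shows what each reading of the present limits implies. The cost is a protocol wording change, with no added patients, visits or staff.
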